#### 3.2. Secondary Endpoints

Safety and tolerability will be assessed by monitoring adverse events (AEs) and concomitant medications, performing physical examinations and clinical laboratory evaluations, measuring vital signs, and performing 12-lead electrocardiograms (ECGs). These safety and tolerability endpoints are deemed adequate to detect any safety signals.

[figure not shown]
#### 4. STUDY DESIGN

This is a Phase 1, open-label, 2-period, fixed-sequence drug-drug interaction study to investigate the effect of multiple oral doses of LOXO-305 on the PK of a single oral dose of repaglinide in healthy subjects.

In Period 1, Day 1, a single 0.5 mg oral dose of repaglinide will be administered in the morning, following a fast of at least 10 hours prior to dosing. In order to mitigate any side effects when dosing with repaglinide on Day 1, on Day -1, subjects will be offered breakfast, lunch, dinner, and an optional snack after dinner. On Day 1, subjects will receive a

standardized light breakfast 15 minutes postdose. In addition, subjects may be provided with up to 16 g of glucose (up to 4 x 4 g chewable tablets) approximately 1-hour post-dose, if needed. Glucose values may be checked for subjects suspected of having low blood sugar or being hypoglycemic by fingerstick glucose tests prior to and/or following administration of glucose tablets at the discretion of the PI (or designee). Blood samples for concentrations of repaglinide in plasma will be collected [CC]

In Period 2, on Days 2 through 11, oral doses of 200 mg LOXO-305 will be administered QD in the morning at the actual time of the Day 1 repaglinide dose (± 1 hour). On Days 2 through 11, subjects will fast for at least 2 hours predose and 1-hour postdose with the exception of Days 2, 6, and 11 where clinical laboratory evaluations are performed, subjects will fast for at least 8 hours predose and 1-hour postdose. On Day 12, 200 mg LOXO-305 and 0.5 mg of repaglinide will be co-administered in the morning at the actual time of the Day 1 repaglinide dose (± 1 hour), following a fast of at least 10 hours prior to dosing. In order to mitigate any side effects when dosing with repaglinide on Day 12, on Day 11, subjects will receive breakfast (2 hours after dosing), lunch, dinner, and an optional snack after dinner. On Day 12, subjects will receive a standardized light breakfast 15 minutes post-LOXO-305 and repaglinide dosing. In addition, subjects may be provided with up to 16 g of glucose (up to 4 x 4 g chewable tablets) approximately 1-hour post-LOXO-305 and repaglinide dosing, if needed. Glucose values may be checked for subjects suspected of having low blood sugar or being hypoglycemic by fingerstick glucose tests prior to and/or following administration of glucose tablets at the discretion of the PI (or designee).

There will be a washout period of 11 days between the dose of repaglinide on Day 1 and the dose of repaglinide on Day 12, respectively.

To assess their eligibility to enter the study, potential subjects will be screened within 28 days (Days 29 to -2) and be admitted to the Clinical Research Unit (CRU) on Day -1 (Check in).

Subjects will be confined at the CRU from the time of Check in (Day -1) until end of treatment (EOT) on Day 16 upon completion of all PK and safety assessments or Early Termination (ET) if the subject discontinues. A follow up phone call will occur for all subjects who received at least 1 dose of study drug (including subjects who are terminated early) 7 days (± 2 days) after EOT or ET. The duration of participation is expected to be approximately 54 days (Screening through follow up phone call).

Replacement subjects may be enrolled only if deemed necessary by the Sponsor.

The start of the study is defined as the date the first subject who is enrolled in the study signs an Informed Consent Form (ICF). Note that enrolled subjects are defined as those subjects who are assigned a dose of study drug; this definition excludes screen failure subjects.

In this study, physical examinations, 12 lead ECGs, vital sign measurements, How Do You Feel? inquiries, clinical chemistry panel, coagulation parameters, hematology panel, urinalysis, and recording of concomitant medications will be performed at specified times during the study.

AEs and serious adverse events (SAEs) will be collected beginning at informed consent. AEs will be reported throughout the study (ie, from signing of the ICF until End of Study [EOS], or until ET if the subject discontinues from the study and does not complete a follow up phone call), either as subject medical history (if the event is reported as beginning prior to signing of the ICF or if the event occurs prior to study drug administration on Day 1 and is assessed as not related to study procedures by the Investigator [or designee]) or as AEs (if the event occurs after signing of the ICF but prior to study drug administration on Day 1 and is assessed as related to study procedures by the Investigator [or designee], or if the event occurs after study drug administration on Day 1 through EOT or ET regardless of relationship to study drug). From EOT or ET through EOS, only AEs assessed as related to study drug by the Investigator (or designee) are to be reported. All SAEs that develop from the time of ICF signing until EOS (or ET, if the subject discontinues from the study and does not complete a follow up phone call) are to be reported.

Study completion is defined as the time of the last subject's follow up.

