From AE data reported following LOXO-305 administration in 10 healthy volunteers in the LOXO-BTK-20014 study, all TEAEs (headache, nausea, and vomiting) were Grade 1 in severity and considered related to LOXO-305. All 3 events were reported by 1 subject and resolved within 1 to 1.5 days (data on file at the time of protocol development). From preliminary AE data reported following LOXO-305 administration in healthy volunteers in the LOXO-BTK-20006 study, all TEAEs (intermittent belching, bloating, insect bite, aphthous ulcer, nausea, intermittent diarrhea (x2), muscle twitch) were Grade 1 in severity and bloating, intermittent diarrhea and intermittent belching were considered related to LOXO-305. All 7 AEs were reported by 3 subjects and all events resolved prior to EOT; data on file at the time of protocol development). From preliminary AE data reported following LOXO-305 administration in healthy volunteers in Cohort 1 of the LOXO-BTK-20017 study, there was 1 TEAE (headache) observed in the 300 mg LOXO-305 cohort which was Grade 1 in severity and considered related to LOXO-305. The event resolved within 2 hours (data on file at the time of protocol development).

There is a potential risk that multiple doses of LOXO-305 may lead to decreases in white blood cells including neutrophils, lymphocytes, monocytes, and eosinophils. Therefore, to mitigate any potential immunosuppressive risks during the ongoing SARS-CoV-2 (COVID-19) pandemic, subjects will remain in the Clinical Research Unit (CRU) for 100 hours postdose (approximately 5 half-lives) which is Day 16 to allow for LOXO-305 elimination. In addition, subject's hematology laboratory results will be reviewed prior to discharge from the CRU. More information about the known and expected benefits, risks, and reasonably anticipated AEs associated with LOXO-305 may be found in the IB. 

The dosing regimen of the oral dose of repaglinide in the current study is consistent with use in DDI studies. Hypoglycemia is a possible side effect; however, subjects will be given breakfast, lunch, dinner, and an optional snack after dinner on the day before dosing and will have a standardized light breakfast (Table 4)15 minutes postdose to mitigate any potential side effects. The potential risk of participating in this study and receiving this drug is well managed by the study set-up and considered negligible.

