#### **5.2.** Study Treatment Administration

In Period 1, Day 1, a single 0.5-mg oral dose of repaglinide will be administered in the morning following a fast of at least 10 hours. To mitigate any side effects when dosing with repaglinide on Day 1, on Day -1, subjects will be offered breakfast, lunch, dinner, and an optional snack after dinner. Subjects will receive a standardized light breakfast (see Section 6.2) 15 minutes postdose. In addition, subjects may be provided with up to 16 g of glucose (up to 4 x 4 g chewable tablets) approximately 1-hour postdose, if needed.

In Period 2, on Days 2 through 11, oral doses of 200 mg LOXO-305 will be administered QD in the morning at the actual time of the Day 1 repaglinide dose ( $\pm$  1 hour). On Days 2 through 11, subjects will fast for at least 2 hours predose and 1-hour postdose with the exception of Days 2, 6, and 11 where clinical laboratory evaluations are performed, subjects will fast for at least 8 hours predose and 1-hour postdose. On Day 12, 200 mg LOXO-305 and 0.5 mg of repaglinide will be co-administered in the morning at the actual time of the Day 1 repaglinide dose ( $\pm$  1 hour), following a fast of at least 10 hours prior to dosing. In order to mitigate any side effects when dosing with repaglinide on Day 12, on Day 11, subjects will receive

<sup>b The manufacturer will be confirmed by the site at the time of drug procurement.

Protocol CONFIDENTIAL

Covance Study: 8425120 Protocol Reference: LOXO-BTK-20016

breakfast (2 hours after dosing), lunch, dinner, and an optional snack after dinner. On Day 12, subjects will receive a standardized light breakfast 15 minutes post-LOXO-305 and repaglinide dosing. In addition, subjects may be provided with up to 16 g of glucose (up to 4 x 4 g chewable tablets) approximately 1-hour post-LOXO-305 and repaglinide dosing, if needed.

All study drugs will be administered orally with approximately 240 mL of water. An additional 100 mL of water may be administered if needed. Water will be restricted for 1-hour predose and 1-hour postdose, with the exception of water administered for dose administration.

Each unit dose will be prepared by qualified CRU staff. Each unit dose container will be appropriately labeled.

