#### 6. CONCOMITANT THERAPIES AND OTHER RESTRICTIONS

## **6.1.** Concomitant Therapies

Paracetamol/acetaminophen (maximum of 2 g/day for up to 3 consecutive days) and glucose (up to 16 g/day [up to 4 x 4 g chewable tablets] on Days 1 and 12 following dosing) are acceptable concomitant medications.

Subjects will refrain from participation in any other investigational study drug trial in which receipt of any investigational drug occurs within 5 half-lives (if known) or 30 days, whichever is longer, prior to Day 1.

All prescription medications and over-the-counter medications (except for paracetamol/acetaminophen and glucose as referenced above) are prohibited for 14 days or 5 half lives (if known), whichever is longer, prior to Day 1 and through EOT or ET, unless deemed acceptable by the Investigator (or designee) and Sponsor. This includes, but is not limited to: moderate or strong CYP3A4 and/or CYP3A5 inhibitors or inducers (including herbal products such as St. John's wort; with the exception of repaglinide administered for the purposes of this study/in accordance with the protocol), strong P-gp inhibitors, proton pump inhibitors, antacids, H2-receptor antagonists, and drugs that prolong QT/QTc interval, herbal products, natural or herbal supplements, and HRT.

Any medication taken by a subject during the course of the study, including details of its dosage, administration, and the reason for its use, will be documented in the eCRF.

The administration of any concomitant medication during the study is prohibited without prior approval of the Investigator (or designee) and Sponsor, unless its use is deemed necessary in a medical emergency. In this case, the use of the concomitant medication will be reported as soon as is practical.

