## 6.2. Diet, Fluid, and Activity Control

Subjects are required to refrain from use of tobacco, smoking cessation products, and nicotine-containing products within 3 months prior to Screening through EOT or ET.

Consumption of foods or beverages containing grapefruit/grapefruit juice or Seville oranges or its juice within 7 days prior to Check-in (Day -1) and through EOT or ET will not be allowed.

Consumption of alcohol- or caffeine-containing foods or beverages within 72 hours prior to Check-in (Day -1) and through EOT or ET will not be allowed.

Subjects will refrain from strenuous exercise from 5 days prior to Check-in (Day -1) and during the period of confinement at the CRU and will otherwise maintain their normal level of physical activity through EOT or ET (ie, should not begin a new exercise program or participate in any unusually strenuous physical exertion).

On Day -1 (depending on the time the subject checks into the CRU), subjects will receive breakfast, lunch, dinner, and an optional snack after dinner. On Day 11, subjects will receive breakfast (2 hours after dosing), lunch, dinner, and an optional snack after dinner. On Day 1

and Day 12, subjects will receive a standardized light breakfast (examples of contents are detailed in Table 4) 15 minutes post-repaglinide dose.

Table 4: Example Standardized Light Breakfast Content

Light Breakfast									
Example 1:									
1 hard-boiled egg 1 small piece of toast with butter 1 small apple or banana									
Example 2:									
1 small bowl of cereal or 1 small bagel with cream chees 1 small apple or banana	e								

For the remainder of the time while confined at the CRU, subjects will receive a standard diet at scheduled times that do not conflict with other study-related activities. All study drugs will be administered orally with approximately 240 mL of water. An additional 100 mL of water may be administered if needed.

Fasting requirement in relation to dosing are described in Section 3.1 and Section 5.2.

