## 7.2.2. Clinical Laboratory Evaluations

Clinical laboratory evaluations (clinical chemistry panel [fasted at least 8 hours; at EOT or ET, subjects are not required to be fasted prior to clinical laboratory evaluations], coagulation parameters, hematology panel, TSH [Screening only], HbA1c [Screening only], eGFR [Screening and Check-in (Day -1)] and UA) will be collected at the timepoints specified in Appendix 4.

Screens for HCV antibody, HbsAg, HBV core antibody, and HIV antibody will be performed at Screening.

Testing for COVID-19 via PCR or equivalent will be performed at the timepoints specified in Appendix 4. Testing for COVID-19 may also be conducted periodically during the subject's CRU confinement, at the discretion of the Investigator (or designee). Further details

regarding COVID-19 testing (including procedures for subjects who test positive at any time

A urine drug screen for selected drugs of abuse (including cotinine and alcohol) will be performed at Screening and repeated at Check-in (Day -1) for all subjects. A serum qualitative pregnancy test (female subjects only [serum quantitative may be used for confirmation if needed]) and an FSH test (post-menopausal female subjects only) will be performed at the timepoints specified in Appendix 4.

throughout CRU confinement) are specified in a separate document.

The number of blood samples and total blood volume required for clinical laboratory evaluations are presented in Appendix 3. A list of the specific evaluations is in Appendix 2.

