- c. Height collected at Screening only, body mass index based on Screening height.
- d. A complete physical examination will be performed at Check-in (Day -1) and an abbreviated physical examination will be performed at EOT (Day 16) or ET.
- e. The 12-lead ECGs will be obtained at Screening and Check-in (Day -1), Day 1 (predose), Day 2 (predose, 2 hours after LOXO-305 dosing), Day 6 (predose and 2 hours after LOXO-305 dosing), Day 12 (predose, and 2 hours after LOXO-305 and repaglinide dosing), and EOT (Day 16, ie, 96 hours after LOXO-305 and repaglinide dosing on Day 12) or ET. When scheduled at the same time as blood draws, 12-lead ECGs should be carried out prior to and as close as possible to having blood drawn. The 12-lead ECGs will be collected after the subject has rested in the supine position for at least 10 minutes. The allowed sampling window for 12-lead ECGs is ± 30 minutes from the nominal timepoint for all postdose 12-lead ECGs and no less than 10 minutes prior to dosing for predose 12-lead ECGs.
- f. Vital sign measurements (supine blood pressure [BP] and pulse rate) will be obtained at Screening and Check-in (Day -1), Day 1 (predose), Day 2 (predose, 2 hours after LOXO-305 dosing), Day 6 (predose and 2 hours after LOXO-305 dosing), Day 12 (predose, and 2 hours after LOXO-305 and repaglinide dosing), and EOT (Day 16, ie, 96 hours after LOXO-305 and repaglinide dosing on Day 12) or ET. When scheduled at the same time as blood draws, vital sign measurements should be carried out prior to and as close as possible to having blood drawn. BP and pulse rate will be measured using the same arm for each reading after the subject has been supine for at least 5 minutes. The allowed sampling window for vital sign measurements is ±30 minutes from the nominal timepoint for all postdose vital sign measurements and no less than 10 minutes prior to dosing for predose vital sign measurements.
- g. Oral temperature and respiratory rate will be obtained at Screening and Check-in (Day -1), and EOT (Day 16) or ET.
- h. Oxygen saturation will be measured via pulse oximetry once at Screening, Check-in (Day -1), predose on Day 1, and EOT (Day 16) or ET. The allowed sampling window for predose oxygen saturation measurements is no less than 10 minutes prior to dosing.
- i. An HDYF? inquiry will be performed at Screening (after the ICF is signed), at Check-in (Day -1), at each postdose vital sign measurement, and at an appropriate time for all other days.

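### In the visible schedule, no glucose reading is planned for all subjects on either repaglinide day, so postdose lowering that nobody suspects would be missed

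*SAP*

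**What the plan says.** Protocol section 1.6 acknowledges the risk and relies on meals to contain it: "Hypoglycemia is a possible side effect; however, subjects will be given breakfast, lunch, dinner, and an optional snack after dinner" on the day before dosing. On the dosing day itself, section 6.2 adds food soon after the dose: "subjects will receive a standardized light breakfast (examples of contents are detailed in Table 4) 15 minutes post-repaglinide dose". Section 5.2 adds a rescue option: "subjects may be provided with up to 16 g of glucose (up to 4 x 4 g chewable tablets) approximately 1-hour postdose, if needed". No glucose value or other criterion for giving the tablets is stated.

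Glucose is part of the clinical chemistry panel (protocol Appendix 2). Section 7.2.2 describes the conditions for that panel: "clinical chemistry panel [fasted at least 8 hours; at EOT or ET, subjects are not required to be fasted". The laboratory row in Appendix 4 is marked at Screening, Day -1, and Days 2, 6, 11, 13 and 15 for subjects who complete. It is blank on Day 1 and Day 12.

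SAP section 4 is the only visible place with a same-day check: "Glucose values may be checked for subjects suspected of having low blood sugar or being hypoglycemic by fingerstick glucose tests". The sentence goes on to allow the fingerstick before and/or after glucose tablets, at the discretion of the principal investigator or designee. The visible protocol text does not mention fingersticks.

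Symptoms are asked about through the HDYF? inquiry. Appendix 4, footnote i, places it "at each postdose vital sign measurement, and at an appropriate time for all other days". Footnote f lists the vital sign times: "Vital sign measurements (supine blood pressure [BP] and pulse rate) will be obtained at Screening and Check-in (Day -1), Day 1 (predose), Day 2" and later days. Day 1 has a predose measurement only; Day 12 has predose and 2 hours.

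**The concern.** The study asks whether LOXO-305 raises exposure to a drug whose named side effect is hypoglycemia. Day 12 is timed to LOXO-305 steady state, when protocol section 3.2 expects inhibition of CYP2C8 to be greatest. Safety and tolerability of the combination is the secondary objective. Yet on the two days when repaglinide is given, a glucose value is obtained only if someone already suspects that it is low. A fall without symptoms in the hours after dosing would leave no trace.

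A smaller issue sits beside this. The rule that ties the symptom inquiry to postdose vital signs gives Day 12 a fixed time and Day 1 none. A difference in reported symptoms between repaglinide alone and the combination could partly reflect when subjects were asked.

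**Working it through.** No power or sample-size formula applies. The check is a count of scheduled events, reconciled with the plan's own totals.

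**1. Reproduce the plan's number of chemistry samples.** Marks in the Appendix 4 laboratory row for a subject who completes: Screening, Day -1, Days 2, 6, 11, 13 and 15. That is 7, equal to the 7 chemistry samples in Appendix 3. Footnote v puts the final panel on Day 15 for completers, so the Day 16 mark applies only to early termination. Extra panels on Days 1 and 12 would have made 9.

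**2. Reproduce the blood volume.** Serology 8 + HbA1c 4 + PK draws 52 × 4 = 208 + laboratory 7 × (4 + 4 + 3) = 77 + pregnancy tests 12 + FSH 4 = 313 mL. This equals the stated 313.0 mL, with shared PK draws counted once as 52. The total leaves no room for an extra venous glucose sample. It cannot rule out fingersticks, which would not appear in that table.

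**3. Overlap with the repaglinide days.** Panels after the first dose: {2, 6, 11, 13, 15}. Repaglinide days: {1, 12}. The overlap is empty: 0 of 5. Protocol section 3.1 independently names Days 2, 6 and 11 as the laboratory days within Days 2 to 11.

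**4. The two days side by side.**

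| | Day 1 | Day 12 |
|---|---|---|
| Repaglinide 0.5 mg | alone | with LOXO-305 200 mg |
| Chemistry panel | none | none |
| Nearest panel before / after | Day -1 / Day 2 | Day 11 / Day 13 |
| Fingerstick | on suspicion only | on suspicion only |
| Postdose vital signs and ECG | none | 2 hours (±30 minutes) |
| Symptom inquiry at a fixed postdose time | none | 2 hours (±30 minutes) |

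The Day 2 and Day 13 panels measure glucose on the day after each dose. They do not cover the hours just after dosing.

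**5. Size of the remedy.** 2 readings × 2 days = 4 fingersticks per subject; 4 × 16 = 64 at most for 16 subjects without replacements. Setting a time for the Day 1 inquiry adds none.

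The documents give no basis for a probability that a low value would be missed, so none is claimed.

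**The case against.** The sponsor made a deliberate choice and gave reasons. Protocol section 1.6 judges the risk well controlled by the study set-up and negligible, and section 2.2.2 regards the safety endpoints as adequate. The exposure is two single 0.5 mg doses 11 days apart, with breakfast at 15 minutes, tablets to hand, confinement, and diabetes excluded. In vitro inhibition of CYP2C8 was weak (section 1.3). These points stand and keep the priority low. They reduce the risk, however, and do not measure glucose.

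A reader might infer that tablets are given with no means of taking a reading. The SAP does not support that: it provides for a fingerstick before and/or after tablets in suspected cases. What is missing is a reading in everyone else, and a stated criterion.

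A reader might also infer that hypoglycemia would go unrecorded. It would not. Symptomatic events are adverse events, subjects may report them at any time, and for any medication taken, protocol section 6.1 requires that the record, "including details of its dosage, administration, and the reason for its use, will be documented in the eCRF". SAP section 8.4 lists those medications.

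Nor is it a fault that discretionary readings are listed and not summarized. They come only from suspected subjects, so a summary would be selective. Likewise, nothing shows that breakfast would differ between the two days for a given subject, so there is no case for a matching rule.

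On the symptom inquiry, nothing prevents staff from asking at 2 hours on Day 1, so unequal timing is possible but not shown. No inferential safety comparison is planned. The windows for assigning related adverse events (SAP section 8.6.1) already differ much more: one day for repaglinide alone, against everything from Day 12 dosing onward for the combination. The asymmetry is minor, but removing it is free.

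Finally, one Appendix 4 row is redacted and footnote o survives only in part, so a hidden reading cannot be wholly excluded. The on-suspicion wording in the SAP makes one unlikely, since such a provision would add little if every subject were already being tested.

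**Conclusion.** The concern holds for the visible schedule. Planned glucose readings for all subjects number 0 on Day 1 and 0 on Day 12, and 0 of the 5 later panels fall on a repaglinide day. Postdose lowering that nobody suspects would be missed. Symptom inquiries with a fixed postdose time number 0 on Day 1 and 1 on Day 12.

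This is a low-priority safety-monitoring gap. It does not touch the primary PK comparison, and it does not show that subjects are at undue risk. A reader might take an absence of hypoglycemia reports as evidence that glucose was unaffected; the plan as written cannot support that inference. The conclusion rests on the redacted or missing parts of Appendix 4 holding no scheduled glucose reading.

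**What to change.** 1. In protocol Appendix 4, set the Day 1 symptom inquiry at 2 hours postdose, to match Day 12. This costs nothing.
2. Add a fingerstick for all subjects on Days 1 and 12, just before the tablet decision at about 1 hour and again at 2 hours, alongside PK draws where the times coincide. The investigator and sponsor should state beforehand the reading at which tablets are given; the documents offer no value.
3. Add a sentence to SAP section 8.6.2 to summarize these scheduled values descriptively by treatment and timepoint. Otherwise section 8.6.5 would leave them as listings only.

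The cost is a short protocol amendment, one SAP sentence, and 4 fingersticks per subject by a method that the SAP already allows. The values will reflect breakfast and any tablets, and the first reading may itself prompt tablets. They therefore serve as a safety check and not as a pharmacodynamic comparison. Breakfast and tablet timing stay unchanged.

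If dosing is complete, the clinical study report should say that asymptomatic postdose glucose lowering was not systematically assessed.
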